### APPENDIX 3. STRONG CYP3A4 INHIBITORS AND INDUCERS AND CYP3A SENSITIVE SUBSTRATES

To avoid possible drug-drug interactions, strong inhibitors and inducers of CYP3A4 and CYP3A sensitive substrates should be avoided in patients receiving cerdulatinib (Table A3-9 and Table A3-10). If the Investigator feels that use of these medications is necessary, this should be discussed with the Medical Monitor. A dose adjustment (lowering) for CYP3A sensitive substrates may be considered on a case-by-case basis.

**Table A3-9: Strong CYP3A4 Inhibitors and Inducers**

Strong Inhibitors	Strong Inducers
Clarithromycin	Barbiturates
Telithromycin	Efavirenz
Ketoconazole and Posaconazole	Nevaripine
Itraconazole	Pioglitazone
Fluvoxamine	Rifampin
Nefazodone	Rifabutin
Ritonavir, Lopinavir	Carbamazepine
Indinavir	Phenytoin
Nelfinavir	Modafinil
Sequinavir	St. John's Wort
Atazanavir	
Grapefruit/Grapefruit Juice	

**Table A3-10: CYP3A Sensitive Substrates**

Generic (Trade Name)	
Albendazole (Albenza®)	Levomilnacipran (Fetzima®)
Alfentanil (Alfenta®) - drug has narrow therapeutic index	Lopinavir and Ritonavir (Kaletra®)
Aliskiren (Tekturna®)	Lovastatin (Mevacor®)
Almotriptan (Axert®)	Lurasidone (Latuda®)
Alprazolam (Xanax®)	Maraviroc (Selzentry®)
Aprepitant (Emend®)	Medroxyprogesterone acetate (Depo-Provera®)
Aripiprazole (Abilify®)	Methadone
Avanafil (Stendra®)	Midazolam (Versed®)
Brexpiprazole (Rexulti®)	Mirtazapine (Remeron®)
Bromocriptine (Cycloset®, Parlodel®)	Nevirapine (Viramune®)
Budesonide (Entocort®, Pulmicort®)	Nisoldipine (Sular®)
Buprenorphine (Suboxone®, Butrans®, etc.)	Ospemifene (Osphena®)

Generic (Trade Name)	
Buspirone (Buspar®)	Oxycodone (Percocet®, Oxycontin®)
Cariprazine (Vraylar®)	Paritaprevir (Viekira Pak™, Technivie™) - major substrate
Clonazepam (Klonopin®) (probable)	Pimozide (Orap®) - drug has narrow therapeutic index
Conivaptan (Vaprisol®)	Praziquantel (Biltricide®)
Cyclophosphamide (Cytosan®)	Propafenone (Rythmol®)
Cyclosporine (Neoral®, Gengraf®, Sandimmune®) - drug has narrow therapeutic index	Quetiapine (Seroquel®)
Daclatasvir (Daklinza™)	Quinidine - drug has narrow therapeutic index
Darifenacin (Enablex®)	Roflumilast (Daliresp®)
Darunavir (Prezista®)	Salmeterol (Serevent®)
Dasatinib (Sprycel®)	Saquinavir (Invirase®)
Diazepam (Valium®)	Sildenafil (Viagra®)
Dienogest (progesterone in oral contraceptives)	Simeprevir (Olysio®)
Dihydroergotamine (DHE-45®, Migranal®) – drug has narrow therapeutic index	Simvastatin (Zocor®)
Dronedarone (Multaq®)	Sirolimus (Rapamune®) - drug has narrow therapeutic index
Drospirenone (progesterone in oral contraceptives)	Suvorexant (Belsomra®)
Elbasvir (Zepatier®)	Tacrolimus (Prograf®) - drug has narrow therapeutic index
Eletriptan (Relpax®)	Tadalafil (Cialis®)
Eplerenone (Inspra®)	Tamsulosin (Flomax®)
Ergotamine (Cafegot®)	Temsirolimus (Torisel®)
Eszopiclone (Lunesta®)	Ticagrelor (Brilinta®)
Ethinyl Estradiol (oral contraceptives, Ortho Evra®, NuvaRing®)	Tinidazole (Tindamax®)
Etonogestrel (Implanon®, Nexplanon®, NuvaRing®)	Tofacitinib (Xeljanz®) (major substrate)
Everolimus (Afinitor®)	Tolvaptan (Samsca®)
Felodipine (Plendil®)	Tipranavir (Aptivus®)
Fentanyl (Duragesic®) - drug has narrow therapeutic index	Triazolam (Halcion®)
Flibanserin (Addyi®) - major substrate	Vardenafil (Levitra®)
Fluticasone (Flovent®, Arnuity Ellipta®)	Verapamil (Calan®, Covera-HS®, Verelan®, etc.)
Grazoprevir (Zepatier®)	Vilanterol (Anoro Ellipta®)
Guanfacine (Intuniv®)	Vilazodone (Viibryd®)
Hydrocodone (Norco®, Vicodin®, etc.)	Vorapaxar (Zontivity®)
Iloperidone (Fanapt®)	Zolpidem (Ambien®)
Indinavir (Crixivan®)	Levomilnacipran (Fetzima®)
Lapatinib (Tykerb®)	Lopinavir and Ritonavir (Kaletra®)

## APPENDIX 4. RESPONSE DEFINITIONS FOR B-CELL NHL AND PTCL, CLL, AND CTCL

### 1. Response Criteria for NHL

Radiographic (including PET scan) and clinical assessments will be evaluated in accordance with The Lugano Classification [4]. The criteria are summarized in [Table A4-11](#).

PET-CT is preferred for FDG-avid lymphomas and CT scan is preferred in other lymphomas. For patients staged with PET-CT, focal uptake in nodal and extranodal sites that is in keeping with lymphoma, according to the distribution and/or CT characteristics, is considered involvement with lymphoma, including spleen, liver, bone, thyroid, etc.

For patients staged with CT:

- Selection of target (measured) lesions is as follows:
  - Up to 6 of the largest nodes, nodal masses, and extranodal lesions selected to be clearly measurable in 2 diameters:
  - A measurable node must have a longest transverse diameter of a lesion (LDi) > 1.5 cm.
  - A measurable extranodal lesion (e.g., hepatic nodules) should have an LDi > 1.0 cm.
  - Preferably, nodes should be disparate regions of the body and should include, where applicable, mediastinal and retroperitoneal areas.
  - Non-nodal lesions include those in solid organs (e.g., liver, spleen, kidneys, and lungs), gastrointestinal (GI) involvement, cutaneous lesions, or those noted on palpation. If possible, they should:
    - Be from disparate regions of the body.
    - Include mediastinal and retroperitoneal areas of disease whenever these sites are involved.
- Selection of non-target (non-measured) lesions:
  - Any lesions not selected as target (measured) and truly assessable lesions should be considered not measured.
  - These lesions include any nodes, nodal masses, and extranodal lesions not selected as target (measured) or that do not meet the requirements for measurability but are still considered abnormal, as well as truly assessable lesions, which are any sites of suspected disease that would be difficult to follow quantitatively with measurement, (e.g., cutaneous, GI, bone, spleen, liver, kidneys, pleural or pericardial effusions, ascites, leptomeningeal lesions/disease) and other lesions that cannot be confirmed and followed by imaging.

**Table A4-11: Lugano Criteria [4] (Revised Criteria) for Response Assessment in NHL**

Response and Site	PET-CT–Based Response	CT-Based Response

Complete
 
Lymph nodes and extralymphatic sites
 
Nonmeasured lesion
 
Organ enlargement
 
New lesions
 
Bone marrow
	
Complete metabolic response
 
Score 1, 2, or 3 a with or without a residual mass on 5PS b
 
It is recognized that in Waldeyer’s ring or extranodal sites with high physiologic uptake or with activation within spleen or marrow (e.g., with chemotherapy or myeloid colony-stimulating factors), uptake may be greater than normal mediastinum and/or liver. In this circumstance, complete metabolic response may be inferred if uptake at sites of initial involvement is no greater than surrounding normal tissue even if the tissue has high physiologic uptake.
 
Not applicable
 
Not applicable
 
None
 
No evidence of FDG-avid disease in marrow
	
Complete radiologic response (all of the following):
 
Target nodes/nodal masses must regress to < 1.5 cm in LDi No extralymphatic sites of disease.
 
Absent
 
Regress to normal
 
None
 
Normal by morphology; if indeterminate, IHC negative

Partial
 
Lymph nodes and extralymphatic sites
	
Partial metabolic response
 
Score 4 or 5 b with reduced uptake compared with baseline and residual mass(es) of any size:
 
At interim, these findings suggest responding disease.
 
At end of treatment, these findings indicate residual disease.
	
Partial remission (all of the following):
 
> 50% decrease in SPD of up to 6 target measurable nodes and extranodal sites.
 
When a lesion is too small to measure on CT, assign 5 mm × 5 mm as the default value.
 
When no longer visible, 0 × 0 mm.
 
For a node > 5 mm × 5 mm, but smaller than normal, use actual measurement for calculation.


Nonmeasured lesions
 
Organ enlargement
 
New lesions
 
Bone marrow
	
Not applicable
 
Not applicable
 
None
 
Residual uptake higher than uptake in normal marrow but reduced compared with baseline (diffuse uptake compatible with reactive changes from chemotherapy allowed). If there are persistent focal changes in the marrow in the context of a nodal response, consideration should be given to further evaluation with MRI or biopsy or an interval scan.
	
Absent/normal, regressed, but no increase.
 
Spleen must have regressed by > 50% in length beyond normal.
 
None
 
Not applicable

Cerdulatinib

Response and Site	PET-CT–Based Response	CT-Based Response

No response or stable disease Target nodes/nodal masses, extranodal lesions
 
Nonmeasured lesions Organ enlargement New lesions Bone marrow
	
No metabolic response Score 4 or 5 with no significant change in FDG uptake from baseline at interim or end of treatment
 
Not applicable Not applicable None No change from baseline
	
Stable disease < 50% decrease from baseline in SPD of up to 6 dominant, measurable nodes and extranodal sites; no criteria for progressive disease are met
 
No increase consistent with progression No increase consistent with progression None Not applicable

Progressive disease
 
Individual target nodes/nodal masses Extranodal lesions
 
Nonmeasured lesions
	
Progressive metabolic disease
 
Score 4 or 5 with an increase in intensity of uptake from baseline and/or New FDG-avid foci consistent with lymphoma at interim or end-of-treatment assessment
 
None
	
Progressive disease requires at least 1 of the following PPD progression: An individual node/lesion must be abnormal with: LDi > 1.5 cm, and Increase by > 50% from PPD nadir and an increase in LDi or SDi from nadir 0.5 cm for lesions < 2 cm 1.0 cm for lesions > 2 cm In the setting of splenomegaly, the splenic length must increase by > 50% of the extent of its prior increase beyond baseline (e.g., a 15-cm spleen must increase to > 16 cm). If no prior splenomegaly, must increase by at least 2 cm from baseline New or recurrent splenomegaly New or clear progression of preexisting nonmeasured lesions

Response and Site	PET-CT–Based Response	CT-Based Response
New lesions	New FDG-avid foci consistent with lymphoma rather than another etiology (e.g., infection, inflammation). If uncertain regarding etiology of new lesions, biopsy or interval scan may be considered.	Regrowth of previously resolved lesions A new node > 15 cm in any axis A new extranodal site > 1.0 cm in any axis; if < 1.0 cm in any axis, its presence must be unequivocal and must be attributable to lymphoma Assessable disease of any size unequivocally attributable to lymphoma New or recurrent lymphoma

5PS = 5-point scale; CT = Computed tomography; FDG = Fluorodeoxyglucose; GI = Gastrointestinal; IHC = Immunohistochemistry; LDi = Longest transverse diameter of a lesion; MRI = Magnetic resonance imaging; PET = Positron emission tomography; PPD = Cross product of the LDi and perpendicular diameter; SDi = Shortest axis perpendicular to the LDi; SPD = Sum of the product of the perpendicular diameters for multiple lesion

a A score of 3 in many patients indicates a good prognosis with standard treatment, especially if at the time of an interim scan. However, in trials involving PET where de-escalation is investigated, it may be preferable to consider a score of 3 as inadequate response (to avoid under treatment). Measured dominant lesions: Up to six of the largest dominant nodes, nodal masses, and extranodal lesions selected to be clearly measurable in two diameters. Nodes should preferably be from disparate regions of the body and should include, where applicable, mediastinal and retroperitoneal areas. Non-nodal lesions include those in solid organs (e.g., liver, spleen, kidneys, lungs), GI involvement, cutaneous lesions, or those noted on palpation. Nonmeasured lesions: Any disease not selected as measured, dominant disease and truly assessable disease should be considered not measured. These sites include any nodes, nodal masses, and extranodal sites not selected as dominant or measurable or that do not meet the requirements for measurability but are still considered abnormal, as well as truly assessable disease, which is any site of suspected disease that would be difficult to follow quantitatively with measurement, including pleural effusions, ascites, bone lesions, leptomeningeal disease, abdominal masses, and other lesions that cannot be confirmed and followed by imaging. In Waldeyer's ring or in extranodal sites (e.g., GI tract, liver, bone marrow), FDG uptake may be greater than in the mediastinum with complete metabolic response, but should be no higher than surrounding normal physiologic uptake (e.g., with marrow activation as a result of chemotherapy or myeloid growth factors).

b PET 5PS: 1, no uptake above background; 2, uptake < mediastinum; 3, uptake > mediastinum but < liver; 4, uptake moderately > liver; 5, uptake markedly higher than liver and/or new lesions; X, new areas of uptake unlikely to be related to lymphoma.

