*Note: CLL patients only: ANC  $\geq 750/\mu\text{L}$  and platelet count  $\geq 30,000/\mu\text{L}$  are acceptable. There are no limits on ANC or platelet count required for patients with leukemic forms of PTCL (ATLL, PLL, LGL) or HSTCL as long as cytopenia, if present, is secondary to disease.*

8. Patient must have adequate renal function as evidenced by a creatinine clearance  $\geq 30$  mL/min (calculated using the Cockcroft-Gault equation or based on a 24-hour urine specimen).
9. Patient must have adequate hepatic function as evidenced by a serum bilirubin level  $\leq 2.0$  mg/dL AND serum AST/ALT levels  $\leq 2.5\times$  the ULN for the reference lab. Serum bilirubin  $\leq 2.5$  mg/dL when increase clearly documented as due to Gilbert's syndrome.
10. Where available, ability to submit a formalin-fixed paraffin embedded tissue (FFPE) block or a minimum of 10 unstained, freshly cut FFPE tissue slides from lymph node or other biopsies that were collected as part of patient diagnosis. If samples are unavailable the patient is still eligible for enrollment.
11. Measureable disease for a given tumor type, defined as:
  - a. The presence of  $\geq 1$  lesion that measures  $\geq 1.5$  cm in a single dimension as assessed by CT, CT/PET for patients with nodal or mass lesions (e.g., FL, DLBCL, other NHL), or
  - b. Quantifiable circulating tumor cells for patients with circulating tumor (e.g., Sézary Syndrome [SS]), or
  - c. For CTCL: mSWAT score  $> 0$ .

12. Ability to provide redacted copies of pathology reports and radiology reports used for the diagnosis of NHL or CLL. In addition, for CTCL, ability to provide redacted photographs of skin responses.

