## 6. Progressive Disease (PD)

- The occurrence of any of the following events indicates definitive PD:  
Evidence of any new disease that was not present as baseline:
- A new node that measures  $> 1.5$  cm in any diameter
- A new node that measures  $> 1.0$  cm to  $\geq 1.5$  cm in the longest diameter and  $> 1.0$  cm in the longest perpendicular diameter
- New hepatomegaly or splenomegaly
- New non-target disease (e.g., effusions, ascites, or other organ abnormalities related to CLL)

**Note:** Isolated new effusions, ascites, or other organ abnormalities are not sufficient evidence alone of PD unless histologically confirmed. Thus, a declaration of PD should not be made if this is the only manifestation of apparently new disease.

- Evidence of worsening of lymph nodes, spleen or liver, or non-target disease:
  - Increase by  $\geq 50\%$  from the nadir in the SPD of target lesions.

- Increase by  $\geq 50\%$  from the nadir in the product of the perpendicular diameters for any individual node; progression of a single lesion requires that the lesion demonstrates a  $\geq 50\%$  in the product of its diameters and that the lesion now meets the definition of abnormal (a node that was considered large at baseline must now measure  $> 1.5$  cm in the longest diameter and a node that was considered small at baseline must now measure  $> 1.0$  cm in the longest diameter perpendicular to the long diameter of the lesion).
- Increase by  $\geq 50\%$  from the nadir in the longest diameter for any individual node if the node now has a longest perpendicular diameter that is  $> 1.0$  cm.
- In a patient with an abnormal spleen, an increase by  $\geq 50\%$  from the nadir enlargement of the spleen vertical dimension below the left costal margin (by palpation) or in total vertical dimension (by imaging).
- In a patient with an abnormal liver, an increase by  $\geq 50\%$  from the nadir enlargement of the liver total vertical dimension at the right costal margin (by percussion) or a unequivocal qualitative increase in liver size (by imaging).
- Unequivocal increase in the size of non-target disease (e.g., effusions, ascites, or other organ abnormalities related to CLL).
- Transformation to a more aggressive histology (e.g., Richter syndrome) as established histologically.

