If the start day of a subsequent anti-cancer therapy is missing, it will be assumed to be the first day of the month.

5. Cancer Diagnosis

If a cancer diagnosis date is partially missing, impute as follows:

- If both month and day are missing, the imputed value will be Jan 1
- If only day is missing, the imputed day will be the first day of the month
- If end date is completely missing, do not impute

6. Prior Therapy/Response to Prior Therapy

If the day of a prior therapy or response to prior therapy date is missing, set it to 15th of the month. Otherwise, do not impute.

B. Pathology subgroup of Peripheral T-cell Lymphoma (PTCL)

CSR TFL Column	Pathology in EDC
AITL/TFH	AITCL
	PTCL Angioimmunoblastic T-Cell Lymphoma (AITL)
	PTCL with T-follicular helper phenotype
NOS	PTCL (Peripheral T-Cell Lymphoma) -NOS
Others	ATLL
	ATLL
	ATLL, HTLV-1 associated
	CD4+ PTCL, skin only
	CD4+ PTCL, skin-only
	Cutaneous Gamma Delta
	Cutaneous gamma-delta T-cell Lymphoma
	G/D TCL, skin and LN+
	HTLV-1 ATLL
	Hepatosplenic T cell Lymphoma
	Hepatosplenic T-cell Lymphoma
	LGL*
	Monomorphic Epitheliotropic Intestinal T-Cell Lymphoma
	NK/T-cell
	PTCL Anaplastic Large Cell Lymphoma (ALCL) ALK Negative (-)
	Primary Cutaneous Gamma/Delta T-cell Lymphoma
	T-Cell Prolymphocytic Leukemia
	T-cell prolymphocytic leukemia
	aggressive epidermotropic CD8+ **
	gamma-delta T-cell lymphoma
hepatosplenic T Cell lymphoma	
hepatosplenic gamma-delta T cell lymphoma	

*LGL (large granular lymphocytic leukemia) was miscategorized as PTCL at study entry

**CTCL with aggressive epidermotropic CD8+ was miscategorized as PTCL at study entry

C. Lugano Criteria for Response Assessments in NHL (Protocol Amendment 9 Table A4-11).

Response and Site	PET-CT–Based Response	CT-Based Response

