
Complete
 
Lymph nodes and extralymphatic sites
 
Nonmeasured lesion
 
Organ enlargement
 
New lesions
 
Bone marrow
	
Complete metabolic response
 
Score 1, 2, or 3^a with or without a residual mass on 5PS^b
 
It is recognized that in Waldeyer’s ring or extranodal sites with high physiologic uptake or with activation within spleen or marrow (e.g., with chemotherapy or myeloid colony-stimulating factors), uptake may be greater than normal mediastinum and/or liver. In this circumstance, complete metabolic response may be inferred if uptake at sites of initial involvement is no greater than surrounding normal tissue even if the tissue has high physiologic uptake.
 
Not applicable
 
Not applicable
 
None
 
No evidence of FDG-avid disease in marrow
	
Complete radiologic response (all of the following):
 
Target nodes/nodal masses must regress to < 1.5 cm in LDi No extralymphatic sites of disease.
 
Absent
 
Regress to normal
 
None
 
Normal by morphology; if indeterminate, IHC negative

Partial
 
Lymph nodes and extralymphatic sites
	
Partial metabolic response
 
Score 4 or 5^b with reduced uptake compared with baseline and residual mass(es) of any size:
 
At interim, these findings suggest responding disease.
 
At end of treatment, these findings indicate residual disease.
	
Partial remission (all of the following):
 
> 50% decrease in SPD of up to 6 target measurable nodes and extranodal sites.
 
When a lesion is too small to measure on CT, assign 5 mm × 5 mm as the default value.
 
When no longer visible, 0 × 0 mm.
 
For a node > 5 mm × 5 mm, but smaller than normal, use actual measurement for calculation.

Nonmeasured lesions
 
Organ enlargement
 
New lesions
 
Bone marrow
	
Not applicable
 
Not applicable
 
None
 
Residual uptake higher than uptake in normal marrow but reduced compared with baseline (diffuse uptake compatible with reactive changes from chemotherapy allowed). If there are persistent focal changes in the marrow in the context of a nodal response, consideration should be given to further evaluation with MRI or biopsy or an interval scan.
	
Absent/normal, regressed, but no increase.
 
Spleen must have regressed by > 50% in length beyond normal.
 
None
 
Not applicable

Response and Site	PET-CT–Based Response	CT-Based Response

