No response or stable disease Target nodes/nodal masses, extranodal lesions Nonmeasured lesions Organ enlargement New lesions Bone marrow	No metabolic response Score 4 or 5 with no significant change in FDG uptake from baseline at interim or end of treatment Not applicable Not applicable None No change from baseline	Stable disease < 50% decrease from baseline in SPD of up to 6 dominant, measurable nodes and extranodal sites; no criteria for progressive disease are met No increase consistent with progression No increase consistent with progression None Not applicable
Progressive disease Individual target nodes/nodal masses Extranodal lesions Nonmeasured lesions	Progressive metabolic disease Score 4 or 5 with an increase in intensity of uptake from baseline and/or New FDG-avid foci consistent with lymphoma at interim or end-of-treatment assessment None	Progressive disease requires at least 1 of the following PPD progression: An individual node/lesion must be abnormal with: LDi > 1.5 cm, and Increase by > 50% from PPD nadir and an increase in LDi or SDi from nadir 0.5 cm for lesions < 2 cm 1.0 cm for lesions > 2 cm In the setting of splenomegaly, the splenic length must increase by > 50% of the extent of its prior increase beyond baseline (e.g., a 15-cm spleen must increase to > 16 cm). If no prior splenomegaly, must increase by at least 2 cm from baseline New or recurrent splenomegaly New or clear progression of preexisting nonmeasured lesions
New lesions	New FDG-avid foci consistent with lymphoma rather than another etiology (e.g., infection, inflammation). If uncertain regarding etiology of new lesions, biopsy or interval scan may be considered.	Regrowth of previously resolved lesions A new node > 15 cm in any axis A new extranodal site > 1.0 cm in any axis; if < 1.0 cm in any axis, its presence must be unequivocal and must be attributable to lymphoma Assessable disease of any size unequivocally attributable to lymphoma New or recurrent lymphoma

5PS = 5-point scale; CT = Computed tomography; FDG = Fluorodeoxyglucose; GI = Gastrointestinal; IHC = Immunohistochemistry; LDi = Longest transverse diameter of a lesion; MRI = Magnetic resonance imaging; PET = Positron emission tomography; PPD = Cross product of the LDi and perpendicular diameter; SDi = Shortest axis perpendicular to the LDi; SPD = Sum of the product of the perpendicular diameters for multiple lesion

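### The CT new-node limit for progression is printed as 15 cm in both protocol and SAP, ten times the 1.5 cm nodal limit used elsewhere, so progression on CT-only scans can be called and dated inconsistently

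*Protocol*

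**What the plan says.** Protocol Appendix 4, Table A4-11, sets out the Lugano response criteria for NHL. In the CT column, the new-lesions cell for progressive disease contains the line "A new node > 15 cm in any axis". SAP Appendix C repeats the table, and the line with it, under the title "Lugano Criteria for Response Assessments in NHL (Protocol Amendment 9 Table A4-11"). This is therefore one figure carried over, not two independent statements.

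Other nodal limits in the documents are 1.5 cm:

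- Entry (Protocol 4.1.2, item 11a): a lesion of at least 1.5 "cm in a single dimension as assessed by CT, CT/PET for patients with nodal or mass lesions".
- Measurability (Protocol Appendix 4, section 1): "A measurable node must have a longest transverse diameter of a lesion (LDi) > 1.5 cm".
- CT complete response (same table, both documents): "Target nodes/nodal masses must regress to < 1.5 cm in LDi".
- CT progression of an existing node (same table, both documents): "An individual node/lesion must be abnormal with: LDi > 1.5 cm".
- New node in CLL (Protocol Appendix 4, section 6): more than 1.5 cm in any diameter.
- New node in CTCL (Protocol Table A4-16): more than 1.5 cm in the long axis.

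The line after the new-node line reads "A new extranodal site > 1.0 cm in any axis".

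SAP 7.8.2.1 defines the PFS event as investigator-assessed progression and refers to Appendix C. SAP 7.8.2.2 applies the PFS censoring and analysis conventions to DOR.

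**The concern.** A new node of, say, 3 cm is twice the size that makes a node measurable at baseline, yet it does not meet the printed new-node line. It does not fit any better category either, because CR, PR and SD on CT all require that there be no new lesions. The cell thus places an explicit numeric limit for new nodes beside lines that rest on judgement. Two investigators looking at the same CT could reach different calls, or the same call on different dates.

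What is at stake is the date of progression on CT-only assessments, and through it PFS and, in responders, DOR. If new anti-cancer therapy starts before progression is recorded, SAP Table 1 turns what would have been an event into an observation censored at the last disease assessment on or before that therapy.

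**Working it through.** **Size of the discrepancy**

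| Comparison | Limit | Ratio to printed 15 cm |
|---|---|---|
| Nodal limit elsewhere | 1.5 cm | 15 / 1.5 = 10 |
| New extranodal site, same cell | 1.0 cm | 15 / 1.0 = 15 |
| Bulky-disease cut-off, SAP 7.4 and 7.8.3 | 7 cm | 15 / 7 = 2.14 |

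Measurability for the same two lesion types (Protocol Appendix 4, section 1) is 1.5 cm for nodes and 1.0 cm for extranodal lesions. With 1.5 cm in the new-node line, the two lines of the cell would reproduce that pair. The decimals around the line (0.5, 1.0, 1.5 cm) are intact in both documents, which argues against a mere text-conversion loss but does not exclude it.

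**Can a new node of 1.5 to 15 cm still be called progression?** Yes. Meeting one listed item is enough, and the 15 cm line is only one of them. The alternatives are:

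- assessable disease of any size clearly due to lymphoma;
- new or recurrent lymphoma;
- regrowth, if the site had previously resolved;
- arguably the nonmeasured-lesion line, since footnote a counts nodes not selected as measured.

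The 15 cm line does not block progression. It conflicts with the other routes to it.

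**Delay per affected patient if progression is first recorded one scan later**

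- Disease assessments are every 3 cycles (Protocol 7.3.2) of 28 days (Protocol 7.3.3.1): 3 × 28 = 84 days. With the SAP's conversion factor, 84 / 30.4375 = 2.76 months.
- Appendix 1 allows the CT up to 7 days before the visit. If that is used at only one of the two visits, and visits are on schedule, the range is 84 − 7 = 77 days (2.53 months) to 84 + 7 = 91 days (2.99 months).
- Protocol 3.1.5 states an 8 to 12 week interval. Its lower end is 8 × 7 = 56 days, or 56 / 30.4375 = 1.84 months. From Cycle 3 onward the Appendix 1 schedule gives 84 days, so 84 is the relevant nominal figure there.
- The delay is 0 days if the reader used another progression line or 1.5 cm, and shorter than the scheduled interval if an unscheduled scan is done.

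**Scope**

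- SAP section 8 limits aggregated efficacy to FL in Cohorts 1 and 2 and PTCL in Cohort 5.
- PET-CT-based assessments and the CLL and CTCL criteria do not use this line.
- Dominant mass response (SAP 7.8.2.5) and the waterfall plot (SAP 7.8.2.6) use target lesions only and are unaffected.
- Leukemic PTCL is unclear. Protocol 8.1 gives it separate criteria. The SAP defines response by Lugano, reproduces only that table, and lists ATLL, T-cell prolymphocytic leukemia and LGL in the PTCL Others group of Appendix B, without stating the exemption.

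**The case against.** The strongest reply is that the table contains its own remedy. A new lymphomatous node cannot be CR, PR or SD, and it satisfies at least one size-free progression line, so the table read as a whole gives progression at that scan. The table is also described as a summary of the Lugano classification, which investigators know. Progression is their call, and no program derives it from 15 cm. PET-CT is preferred for FDG-avid lymphomas, the share of CT-only assessments is unknown, and nothing shows that anyone applied the 15 cm line alone. On this view it is a minor erratum, and a data query is excessive.

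Most of this stands, and it limits the consequence: there is no basis for claiming systematic missed progression, a measurable bias in PFS, or an effect on ORR. The 77 to 91 day range also leaves out the ±3-day visit window, so the delay figures are illustrative.

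It does not make the line harmless. The printed number is the only explicit size rule for a new node on CT in NHL, and the SAP cites this table for the PFS event. A reader who applies the number and one who applies the size-free lines can differ, and the documents do not say which prevails.

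**Conclusion.** The concern holds. The new-node limit is wrong by a factor of ten against the documents' own nodal limits, in an operative progression criterion, in both protocol and SAP. The consequence is possible inconsistency in calling and dating progression on CT-only Lugano assessments in FL (Cohorts 1 and 2) and PTCL (Cohort 5).

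Per affected patient the shift ranges from none to nominally 84 days when progression is first recorded at the next scheduled CT. That assumes the 3-cycle schedule is kept and no unscheduled scan is done. How many patients are affected cannot be derived from the documents, so no change in median or landmark PFS is asserted. The point should be fixed because an operative criterion carries a wrong figure, not because a bias has been estimated.

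**What to change.** 1. Check the line in the issued PDFs of both documents.
2. Reconcile the new-node line in Protocol Table A4-11 and SAP Appendix C with the 1.5 cm nodal limit used elsewhere in the documents.
3. Ask sites which threshold they applied.
4. Before database lock, query CT-only assessments in FL (Cohorts 1 and 2) and in PTCL (Cohort 5) assessed by Lugano that record a new node without progression. Include leukemic PTCL only if the sponsor confirms it was assessed by Lugano.

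No new dating rule is needed, because SAP Table 1 already dates progression at the first assessment that shows it. The cost is one figure in two tables, one confirmation from sites, and one data query where the data allow.
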